FINAL REPORT

**EFFECT OF LIRAGLUTIDE ON EPICARDIAL FAT
IN SUBJECTS WITH TYPE 2 DIABETES**

INVESTIGATOR-INITIATED STUDY

NCT 2014740

University of Miami Clinical Trial # 20120811

[name] [name]

Professor of Clinical Medicine

Director of University of Miami Hospital Diabetes Service

Division of Endocrinology, Diabetes and Metabolism, Department of Medicine,
University of Miami, Miller School of Medicine, Miami, FL, USA

[contact]

SUMMARY

Background Epicardial adipose tissue (EAT) is a peculiar visceral fat depot with anatomical and functional contiguity to the myocardium and coronary arteries. EAT is a highly inflammatory tissue enriched with genes involved in endothelial function, coagulation, immune signalling, lipid metabolism, potassium transport and apoptosis. EAT is associated with coronary artery disease, diabetes and obesity. EAT is easily measurable and an emerging therapeutic target that responds and modifies to medications targeting the adipose tissue. Liraglutide, an analogue of glucagon-like peptide-1 (GLP-1), is indicated for the treatment of type 2 diabetes mellitus. Liraglutide has recently shown to reduce cardiovascular risk. Nevertheless, whether liraglutide could reduce EAT is unknown.

Aim The primary objective of this interventional study was to evaluate whether liraglutide can cause a significant and rapid reduction of EAT, organ-specific visceral fat and cardiovascular risk factor itself, in overweight/obese type 2 diabetic patients.

Methods To test this hypothesis we performed a 6-month randomized, open-label, controlled study in 100 type 2 diabetic subjects with body mass index (BMI) $\geq 27 \text{ kg/m}^2$ and HemoglobinA1c (HbA1c) $\leq 8\%$ on metformin monotherapy. Individuals were randomized in 2 groups to receive additional liraglutide up to 1.8 mg sc once daily ($n=55$) or to remain on metformin up to 1000 mg twice daily ($n=45$). Ultrasound-measured EAT thickness was measured at baseline, 3 and 6-month follow ups.

Results In the liraglutide group EAT decreased from 9.6 ± 2 to 6.8 ± 1.5 and 6.2 ± 1.5 mm ($p < 0.001$), accounting for a -29% and -36% of reduction at 3 and 6 months, respectively, whereas there was no EAT reduction in the metformin group; BMI and HbA1c improved only in the liraglutide group after 6 months.

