Patients were enrolled on the basis of the following inclusion criteria: type 2 diabetes, HbA1c $\leq 8\%$ measured at least 1 month prior to the study, BMI $\geq 27 \text{ kg/m}^2$, prior treatment with metformin only, age ≥ 18 and ≤ 65 years old. Exclusion criteria were the following: type 1 diabetes, current use of insulin, other GLP-1 receptor agonists, dipeptidyl peptidase 4 (DPP-4) inhibitors, pramlintide, sulfonylureas, thiazolidinediones, history of diabetic ketoacidosis, history of diabetic macro or micro vascular complications, known contra-indications to liraglutide, such as previous history of pancreatitis or medullary thyroid carcinoma, personal or family history of multiple endocrine neoplasia type 2, renal or liver or heart failure, acute or chronic infective diseases, cancer or chemotherapy, current use of systemic corticosteroids or in the 3 months prior this study, known or suspected allergy to liraglutide, excipients, or related products, pregnant, breast-feeding or the intention of becoming pregnant. Eligible individuals were randomly assigned to receive additional liraglutide, or to remain on metformin. The liraglutide-group was started on liraglutide (Victoza®) up to 1.8 mg s.c. once daily. Liraglutide was administered with a starting dose of 0.6 mg (for a least one week) and subsequent increments to 1.2 mg (after a least one week) and to 1.8 mg (after at least a week on 1.2 mg). Liraglutide-group subjects had to achieve the final dose of 1.8 mg by at least three weeks from the starting dose. Subjects who were not able to tolerate the dose of 1.8 mg, were advised to lower the dose to 1.2 mg. Patients received full training and titration

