Blood Measurements Fasting blood samples for fasting blood glucose (FBG) and HbA1c were obtained from all individuals according to the study design timetable. Blood parameters were measured according to standard and previously described procedures. Fasting comprehensive metabolic panel and lipid profile were also measured at each visit as standard diabetes care.

Follow up of glucose profile Study patients were advised to monitor their capillary glucose twice daily, fasting in the morning and post-prandially. Glucose profile was tracked weekly by the research coordinator and/or principal investigator who were in contact with study patients throughout MyUHealth e-mail system or by telephone.

STATISTICAL ANALYSIS

Primary outcome of the study was EAT changes on liraglutide combined to metformin vs metformin monotherapy; secondary outcomes were determinants of HbA1c changes during treatment. Assuming a difference of 1 ± 0.5 mm in EAT to be clinically significant and using a significance level of $p<0.05$ and 90% power, the current study sample size was sufficient to detect statistical significant differences in EAT between liraglutide and metformin group. Continuous variables were considered as age-adjusted and sex-adjusted means with their standard deviations (SDs). Patients were randomized consecutively using a computer generated randomization table. Two-sample t test with 95 % CI for difference was performed to evaluate differences between the two groups at baseline. Two-way ANOVA was used to calculate changes (Δ) in EAT and other study variables between baseline, 3 and 6 months in both groups. Relations between study variables were calculated using simple linear regression analysis. Two-tailed $p < 0.05$ indicates statistical significance. Statistical analysis was performed using Minitab 17 Software.

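### The primary EAT analysis names only a two-way ANOVA, with no patient term, analysis set or missed-scan rule, so the 6-month estimate is exposed to bias if scans are missing for reasons related to EAT or response

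*Combined protocol and SAP*

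**What the plan says.** The Statistical Analysis section defines the primary outcome as a between-arm comparison: "Primary outcome of the study was EAT changes on liraglutide combined to metformin vs metformin monotherapy". The analysis is given in one sentence: "Two-way ANOVA was used to calculate changes (Δ) in EAT and other study variables between baseline, 3 and 6 months in both groups". The same section says that summary means are adjusted for age and sex.

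The Summary reports that in the liraglutide group "EAT decreased from 9.6 ± 2 to 6.8 ± 1.5 and 6.2 ± 1.5 mm", described as falls of 29% and 36%. For metformin it says only that there was no reduction and gives no means. The arm sizes printed are those randomised, 55 and 45.

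Follow-up scans were scheduled at 3 and 6 months (Study Criteria and Treatment Arms). Nowhere do the documents:

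- define who is analysed;
- say what happens when a scan is missed or unreadable;
- say whether the ANOVA includes patient as a factor, or works on per-patient changes or on visit means;
- give the number scanned at 3 or 6 months, or say that everyone completed.

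**The concern.** The outcome needs repeat scans on the same people, so who contributes to each visit mean matters. The ANOVA sentence can be carried out in at least two ways when a 6-month scan is missing.

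- **Available scans.** The patient counts in the 9.6 mm baseline mean but not in the 6.2 mm mean. The difference then mixes real change with a change in who was measured.
- **Complete cases.** The patient is dropped, along with any usable 3-month scan. The estimate then describes only those who stayed.

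Neither problem depends on patients being analysed outside their allocated arm. The trial is open-label, and only one arm starts a new injected drug, so unequal loss is possible. What is at stake is the size of the effect: the Conclusions make a claim about magnitude, and a reader cannot tell whether the 9.6 and 6.2 mm means come from the same patients.

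**Working it through.** **1. The reported fall.** From the Summary: (9.6 − 6.8)/9.6 = 29.2%, matching 29%. (9.6 − 6.2)/9.6 = 3.4/9.6 = 35.4%. Rounding of the printed means allows 34.6% to 36.3%, so 36% is possible. The arithmetic is sound; the open question is who is in each mean.

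**2. Where bias comes from.** Let *d* be the fraction of the arm with a baseline scan but no 6-month scan. Compare lost with retained patients on the values they would have had at 6 months.

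- Available-scan means overstate the fall by *d* × (mean 6-month EAT of lost − mean 6-month EAT of retained).
- Complete-case change overstates the fall by *d* × (mean fall of retained − mean fall of lost).

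A negative result means understatement. The two readings respond to different gaps, so they can err in opposite directions. If loss is unrelated to EAT and response, both gaps are zero on average and so is the bias.

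Example with assumed values: *d* = 0.20 and lost patients one 6-month SD (1.5 mm) thicker at 6 months gives 0.20 × 1.5 = 0.30 mm overstated by available-scan means. If lost patients would have had a fall 1 mm smaller, complete-case change overstates by 0.20 × 1 = 0.20 mm.

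**3. Simulated size.** Taken from the Summary: liraglutide means 9.6, 6.8 and 6.2 mm, SDs 2, 1.5 and 1.5 mm. Assumed: normal data; between-visit correlation 0.5 or 0.8; 10% or 20% of liraglutide patients without a 6-month scan; log-odds of loss rising by 1 or 2 per SD of the driver; metformin complete and unchanged. The true fall is 3.40 mm.

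| Loss depends on | Available-scan means | Complete-case change | Likelihood model, all scans |
|---|---|---|---|
| thick EAT at 3 months | 3.47–3.71 | 3.29–3.38 | 3.39–3.41 |
| poor response at 3 months | 3.27–3.38 | 3.47–3.71 | 3.40–3.41 |
| poor response at 6 months (unobserved) | 3.37–3.51 | see below | 3.45–3.65 |

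Adding loss that depends on baseline EAT, the ranges over the three observed drivers are 3.27–3.72 mm for available scans, 3.08–3.71 mm for complete cases and 3.40–3.41 mm for the likelihood model. At 5% loss driven by 3-month EAT, available-scan means overstate by only 0.04–0.10 mm.

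A separate simulation of a 55-patient arm used 20% loss and a baseline-to-6-month correlation of 0.3 to 0.8:

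- random loss: 3.40 mm by every method;
- loss related to baseline EAT: available scans 3.48–3.61, completers 3.14–3.26, baseline-adjusted 3.39–3.40;
- loss of poor 6-month responders: available scans 3.38–3.51, completers 3.61–3.77, baseline-adjusted 3.52–3.57.

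**4. Could loss create the effect?** Take the extreme case: no true change, SD 2 mm, and the thickest-EAT patients leaving in strict order. The spurious fall is 2 × φ(z)/(1 − *d*), where z cuts off the top fraction *d*. It is 0.39 mm at 10% loss and 0.70 mm at 20%. Reaching 3.4 mm would need about 89% of the arm lost.

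**The case against.** The strongest reply is that this is a reporting gap and not a demonstrated bias. Much of that stands.

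- A reader might infer that every lost patient biases the result. That is wrong: loss unrelated to EAT or response leaves the estimate at 3.40 mm by every method.
- A reader might infer that the reported 36% is inflated. The documents report no lost patient, and the sign depends on the mechanism: available-scan means overstate the fall when patients with thick EAT leave and understate it when poor 3-month responders leave.
- A reader might take it as settled that unpaired visit means were compared. The sentence speaks of changes, so per-patient changes or a patient factor are not excluded.
- The nearest text on intolerance is "Subjects who were not able to tolerate the dose of 1.8 mg, were advised to lower the dose to 1.2 mg". It describes staying on treatment at a lower dose, not missing a scan. Unequal loss is a possibility, not something the documents show.
- The likelihood model looks near-perfect only where loss depends on scans already observed. Where loss depends on the unseen 6-month response it gives 3.45–3.65 mm, which can be further from the truth than available-scan means. Baseline adjustment alone also removes most of the bias when loss follows 3-month EAT: a complete-case baseline-adjusted analysis gave 3.40–3.49 mm.
- The document is a final report, so changing the model now is post hoc.

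What the reply does not remove is that the plan permits readings that give different answers from the same data, and that nothing printed lets a reader see which was used or whether it mattered.

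**Conclusion.** The point holds as a gap in specification and reporting that carries a risk of bias. If scans are missing for reasons related to EAT or response, either reading can shift the 6-month fall by tenths of a millimetre, up or down. That size rests on an assumed 10–20% loss confined to the liraglutide arm and on assumed correlations and loss mechanisms, because the documents give no loss rate. With no loss or random loss the bias is zero.

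The qualitative conclusion is not in doubt. The plan's yardstick is "Assuming a difference of 1 ± 0.5 mm in EAT to be clinically significant". Taking 0.3 to 0.4 mm off a fall of 3.4 mm leaves 3.4 − 0.4 = 3.0 to 3.4 − 0.3 = 3.1 mm, about three times the 1 mm difference. What is uncertain is the precise magnitude, which the report emphasises. The change should be made, but the trial's direction of effect does not depend on it.

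**What to change.** **In Statistical Analysis**, replace the ANOVA for EAT with wording such as: *All 100 randomised patients are analysed in their allocated arm (55 liraglutide, 45 metformin). EAT is analysed with a likelihood-based repeated-measures model with arm, visit and arm-by-visit terms and within-patient correlation, fitted to every available scan, including those of patients without a 6-month scan. The month-6 between-arm difference is reported with its 95% CI.*

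**Add one sensitivity analysis**, because that model is unbiased only if loss depends on observed data: impute missing month-6 liraglutide values from the metformin arm's change. As a guide to its reach, if completers fell by 3.40 mm and metformin did not change, the estimate would be 0.9 × 3.40 = 3.06 mm at 10% missing and 0.8 × 3.40 = 2.72 mm at 20%.

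**In the Summary**, print the number scanned in each arm at each visit beside each mean. If all 100 patients had all three scans, say so; the sensitivity analysis is then unnecessary.

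**Cost:** a re-run on trial data that the investigators should already hold, labelled as a re-analysis, and a few lines of text. No new patients or procedures are needed. The reported reduction and its interval may change slightly.

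### For the secondary outcome, determinants of HbA1c change, the only method given for relating variables is one-predictor regression, which cannot hold treatment arm or baseline HbA1c alongside a candidate

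*Combined protocol and SAP*

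**What the plan says.** All the analysis text is in the STATISTICAL ANALYSIS section of the combined protocol and SAP. After the primary outcome it states that "secondary outcomes were determinants of HbA1c changes during treatment". It lists no candidate determinants and assigns no model to this outcome.

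On relating one variable to another there is a single sentence: "Relations between study variables were calculated using simple linear regression analysis". It does not say whether the fits pool the two arms or are made within each arm.

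Two other sentences might seem to supply what is missing:

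- "Continuous variables were considered as age-adjusted and sex-adjusted means". This adjusts means for age and sex. It does not mention arm or baseline HbA1c, and it does not concern slopes.
- "Two-way ANOVA was used to calculate changes (Δ) in EAT and other study variables between baseline, 3 and 6 months in both groups". This brings in the groups, but to compare changes across visits, not to relate one change to another.

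The Results paragraph of the SUMMARY says how the two changes behaved: "In the liraglutide group EAT decreased from 9.6 ± 2 to 6.8 ± 1.5 and 6.2 ± 1.5 mm", "whereas there was no EAT reduction in the metformin group", and "BMI and HbA1c improved only in the liraglutide group after 6 months".

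**The concern.** A determinant of HbA1c change should say something about who improves beyond which treatment they received. Simple regression cannot separate the two when the candidate itself moves with treatment. On the reported results, liraglutide patients had both a fall in EAT and an improvement in HbA1c, and metformin patients had neither. A line through all 100 patients can then slope upward merely because it joins two clouds of points, even if nothing relates the two changes inside either cloud. EAT change could be reported as a determinant of glycaemic response when it only marks having received liraglutide.

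The second route does not involve arm. HbA1c change is usually negatively related to its own baseline, partly through regression to the mean. A candidate that tracks baseline HbA1c inherits that relation. Fasting glucose, which the Blood Measurements section collects, is a plausible example. A one-predictor model cannot remove this either.

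What is at stake is the interpretation of the only named secondary outcome.

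**Working it through.** **The plan's own figure.** There is none for the regressions. The sample-size statement concerns the primary comparison. Reading its 1 ± 0.5 mm as a difference and an SD, 2 × (1.96 + 1.28)² × 0.5² / 1² = 5.2, so 6 per arm. The achieved 55 and 45 are therefore ample for that purpose, but this says nothing about the secondary outcome.

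**Inputs from the documents.** 55 and 45 patients; two-sided 0.05; liraglutide EAT 9.6 (SD 2) at baseline and 6.2 (SD 1.5) mm at 6 months, a fall of 3.4 mm; no EAT reduction on metformin; HbA1c improved only on liraglutide.

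**Assumed, because not given.** Correlation ρ between baseline and 6-month EAT; zero mean EAT change and the same SD of change on metformin; the HbA1c effect of arm, d2, in SD units of HbA1c change.

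**Step 1, EAT effect of arm.** SD of change = √(2² + 1.5² − 2ρ × 2 × 1.5), and d1 = 3.4 / SD.

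- ρ = 0: SD 2.50, d1 = 1.36 (about 1.4)
- ρ = 0.5: SD 1.80, d1 = 1.89 (about 1.9)
- ρ = 0.8: SD 1.20, d1 = 2.82 (about 2.8)

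**Step 2, correlation created by arm alone.** With zero correlation inside each arm and k = 0.55 × 0.45 = 0.2475,

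r = k·d1·d2 / √[(1 + k·d1²)(1 + k·d2²)].

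For d1 = 1.89 and d2 = 0.5: 0.234 / √(1.884 × 1.062) = 0.165.

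**Step 3, false-positive rate.** Null simulation, 55 against 45, at least 100,000 trials per cell, pooled simple regression of HbA1c change on EAT change:

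| Assumed HbA1c effect (SD) | d1 = 1.4 | d1 = 1.9 | d1 = 2.8 |
|---|---|---|---|
| 0.1 | 6% | 6% | 7% |
| 0.2 | 8% | 10% | 13% |
| 0.3 | 13% | 17% | 22% |
| 0.5 | 28% | 38% | 51% |
| 0.8 | 58% | 75% | 88% |
| 1.0 | 75% | 90% | 98% |

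With an arm term, or in the liraglutide arm alone, every cell is about 5%. With no HbA1c effect of arm the pooled test also stays at about 5%.

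**Step 4, candidates measured at baseline.** Randomisation makes them independent of arm in expectation, and the pooled rate is 5% at every HbA1c effect. The cost of omitting arm is only power: for an assumed within-arm r of 0.25, 71 / 69 / 64 / 61% at HbA1c effects of 0.3 / 0.5 / 0.8 / 1.0 SD, against about 71% with arm.

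**Step 5, omitting baseline HbA1c.** Let the candidate correlate a with baseline HbA1c, let HbA1c change correlate b with it, and let there be no other link. The induced correlation is a × b. Arm is in the model, and d2 = 0.5.

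| a | b | a × b | Baseline HbA1c omitted | Included |
|---|---|---|---|---|
| 0.3 | −0.3 | −0.09 | 14% | 5% |
| 0.3 | −0.5 | −0.15 | 32% | 5% |
| 0.5 | −0.3 | −0.15 | 32% | 5% |
| 0.5 | −0.5 | −0.25 | 71% | 5% |

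If the candidate is unrelated to baseline HbA1c (a = 0), omission does not inflate error. Inclusion then only narrows the CI: mean half-width 0.202 to 0.193 (about 4%) for b = −0.3, and to 0.175 (about 13%) for b = −0.5.

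**The case against.** The strongest reply is that the arm artefact is not in the text. It needs pooled arms and a post-randomisation candidate, and the section states neither. The regression sentence is not expressly tied to the secondary outcome, and determinants could mean baseline predictors, or changes within the liraglutide arm; for either reading, arm inflates nothing. This stands, and it makes the arm finding conditional. It does not remove it: the section computes changes "in EAT and other study variables between baseline, 3 and 6 months in both groups" and then relates study variables, so EAT change is a natural candidate. The baseline HbA1c problem needs neither condition.

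A second reply is that the pooled association is genuine as a marginal association. That is true. The error would lie in calling it a determinant.

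Third, the rates rest on an HbA1c effect that the documents do not give. This also stands. At 0.1 SD the inflation is trivial, and the upper figures must not be read as estimates. The direction needs only that both changes differ by arm, as the SUMMARY reports.

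Fourth, an arm term does not make EAT change a cause. Under Study Criteria and Treatment Arms, liraglutide patients could end on different doses according to tolerance, so exposure varies within the arm and could drive both changes. This stands and limits what any fix can claim.

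A reader might infer that a spurious determinant has already been reported, or that the EAT result is in doubt. The documents support neither. The SUMMARY reports no regression result, and the primary comparison is between randomised arms and does not use this method.

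**Conclusion.** The concern holds in conditional form. What the text directly shows is that the secondary outcome has no listed candidates, no stated pooling rule and no assigned model, and that the one method offered for relating variables can adjust for neither arm nor baseline HbA1c.

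Two consequences follow:

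- **Arm.** If arms are pooled and the candidate is a post-randomisation change that differs by arm, the false-positive rate exceeds 5% by an amount set mainly by the unknown HbA1c effect, as tabulated. This assumes the same SD of EAT change in both arms and no mean change on metformin.
- **Baseline HbA1c.** A candidate correlated with it can look like a determinant through that correlation alone, at rates of 14 to 71% under the assumed correlations. Baseline HbA1c therefore belongs in the model to control bias as well as to gain precision.

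This is a change worth making to a secondary analysis. It is not a flaw in the primary result.

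**What to change.** For this outcome, replace simple regression with a linear model of 6-month HbA1c change that always includes treatment arm and baseline HbA1c, adding one candidate at a time. In addition:

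- List the candidates, label each as a baseline value or a post-randomisation change, and state that arms are pooled with an arm term.
- Report baseline HbA1c itself from the model with arm only, noting that regression to the mean contributes to its slope.
- Show the arm-by-candidate interaction, or within-arm slopes adjusted for baseline HbA1c, as a check on the common slope.
- Report 95% CIs. Call results for post-randomisation variables associations, not determinants, because confounding within arm remains.

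**Cost.** The data are already collected, so the work is a few sentences and one model per candidate. As the document is a final report, any regression already run must be redone and re-reported.

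The statistical price is precision. For EAT change, the ratio of CI width with an arm term to that in pooled simple regression is √(1 + k·d1²) / √[1 + k·d2² / (1 + k·d1²)]. Over HbA1c effects of 0.3 to 1.0 SD this is 1.21 to 1.13 for d1 = 1.4 and 1.37 to 1.29 for d1 = 1.9, so intervals are about 13 to 37% wider. At d1 = 2.8 the same formula gives roughly 1.7. Fewer variables may then be reported as related.

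Within-arm slopes alone cost more. By r = tanh(2.80 / √(n − 3)), 80% power needs r of about 0.37 with 55 patients or 0.41 with 45, against 0.28 with all 100 and an arm term. They serve better as the check than as the main analysis.
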